### Introduction

Multi-center, 'snapshot' cohort studies or audits have the ability to gather large patient numbers in short time periods from many hospitals. They allow exploration of differences in patients, techniques and management across the cohort to identify areas of practice variability that may result in apparent differences in outcome. As such, whilst not providing true evidence of efficacy or the impact of a particular variable, they can be hypothesis-generating and can identify areas warranting further study in future randomized controlled trials.

The European Society of Trauma and Emergency Surgery has recognized the strengths of this form of research, as well as its power in bringing together surgeons and emergency surgical units across multiple regions or countries for a common research goal, thus strengthening an active network of research participation across Europe.

## Scope

Small bowel obstruction (SBO) and its complications are frequently seen in patients admitted through the Emergency Departments of all acute care hospitals.

[figure not shown]
There is variation in the optimal use of imaging, the appropriate timing and duration of non-operative management attempts, anti-microbial therapies and the criteria for surgical management, which results in heterogeneity in approaches and outcomes across international clinical centers. The expected number of SBO cases in most clinical centers is predictable, enabling a suitable sized cohort of patients to be gathered in the snapshot audit.

This 'ESTES snapshot audit' -a prospective observational cohort study- has a dual purpose. Firstly, as an epidemiological study, it aims to uncover the burden of disease. Secondly, it aims to demonstrate current strategies employed to diagnose and treat these patients. These twin aims will serve to provide a 'snapshot' of what we are doing now, but will also be hypothesis-generating while providing a rich source of patient-level data to allow further analysis of particular clinical question.

# **Key Study Dates**

06 may 2023	Snapshot Launch at ECTES 2023, Ljubljana. Center enrolment and local IRB submission
01 november 2023 - 01 may 2024	Patient enrolment. Ninety (90) consecutive day enrollment within this six (6) month window
01 may 2024	Final day for new patient enrolment
31 July 2024	Final day of patient follow-up (60 days from admission on 01 may 2024)
01 August 2024 - 01 September 2024	Local data validation, completion, and final upload
01 september 2024	REDCap® database locked; this is the deadline for data submission and center inclusion.

### **Definitions**

**Mechanical small bowel obstruction (SBO):** An intrinsic, extrinsic or endoluminal process which narrows or occludes the bowel lumen and delays the passage of luminal contents.

**Ileus:** Functional motility disorder characterized by adynamic paralytic bowel, leading to many of the same symptoms of mechanical obstruction, but without a single site of obstruction demonstrable on imaging. Common causes include recent abdominal surgery, medications such as opiates, and electrolyte disturbances.

**Complete SBO:** Obstruction with no passage of luminal contents beyond the point of obstruction (Appendix A).

**Partial SBO:** Incomplete obstruction with luminal narrowing but some contents continue to pass through the intestine. This is distinguished from complete obstruction by the continued passage of bowel movements and flatus, and a non-peritonitic abdominal exam^3.

**Small bowel dilatation:** Luminal diameter of >3 cm.

**Transition zone:** Short segment area between dilated proximal bowel and decompressed distal bowel. Sometimes called a transition point and is radiographic evidence of SBO.

**Bowel compromise:** when there is ischemia or injury that has led to necrosis and/or perforation of the bowel wall.

**Adhesions:** Fibrous tissue that connects surfaces or organs within the peritoneal cavity that are normally separated. Such adhesions are the results of an adaptive healing response of the peritoneum upon tissue handling or contact with blood or purulence, but also caused by other conditions like radiotherapy, endometriosis, inflammation or local response to tumors.

**Virgin abdomen:** abdomen of a patient without prior surgery. Although there is no consensus in the literature about radiotherapy, known peritoneal inflammatory disease or primary abdominal wall hernias, in our study we will consider only those non-operated inside the definition.

Water Soluble Oral Contrast (WSOC) challenge: a combined diagnostic study and therapeutic intervention utilized in the evaluation and management of small bowel obstruction.

### **Methods**

#### Summary

Prospective audit of consecutive patients admitted in Emergency Department for mechanical small bowel obstruction over a 3 month period. The audit shall include unscheduled patient admissions from November 2023 until May 2024 as outlined in 'Key Study Dates'.

As this is an observational cohort audit, no change to normal patient management is required.

#### **Primary Objective**

To explore differences in patients, management and outcomes across the entire cohort to identify areas of practice variability resulting in apparent differences in outcome warranting further study. The outcomes that the study will examine are:

- Incidence of small bowel obstruction by etiology.
- Differences in clinical presentation.
- Diagnostic work-up.
- Non-operative management strategies.
- Time to surgery and outcomes.
- Complications related to disease and/or therapies within 60 post-operative days.
- Length of Emergency Department and Hospital stay.
- Re-admission within 6 months for related conditions.

#### Methods for identifying patients

Multiple methods may be used according to local circumstances/staffing:

- 1. Daily review of emergency department (non-operative) and operating room lists.
- 2. Daily review of team handover sheets / emergency admission lists / ward lists.
- 3. Review of operating room logbooks.
- 4. Use of electronic systems to flag any readmissions of patients identified and treated.

#### Research Questions

#### **Primary Research Questions**

- What is the global incidence of SBO?
- What are the treatment algorithms currently employed in the management of these patients?
- Proportion of non-operatively managed patients?
- Proportion of surgical patients approached laparoscopically?
- Recurrence rate within 6 months?

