## Data Collection Instrument 10 - Current episode, Final outcome

Current Episode Outcome	Key Name	Data Type	Values
Postoperative Complication	РОСО	Binary	Yes/No (if one at least)
Broncoaspirative pneumonia	BAP	Binary	Yes/No
New Acute Kidney Insufficiency	NAKI	Binary	Yes/No
New Onset Cardiac Arrhythmia	NOCA	Binary	Yes/No
Deep Vein Thrombosis/Pulmonary Embolism	DVT	Binary	Yes/No
Superficial Surgical Site Infection	SSSI	Binary	Yes/No
Deep Surgical Site Infection	DSSI	Binary	Yes/No
Organ Space Surgical Site Infection	OSSSI	Binary	Yes/No
Anastomotic leak	AL	Binary	Yes/No
Reoperation	RELAP	Binary	Yes/No
Most Severe Complication	MSCO	Chain	Named
Clavien Dindo	CLDI	List	I, II, IIIa, IIIb, IVa, IVb, V
ICU	ICU	Binary	Yes/No
ICU Date of Admission	ICUDOA	Date; time	Date of ICU admission dd/mm/yy hh:mm
ICU Date of Discharge	ICUDOD	Date; time	Date of discharge from ICU dd/mm/yy h:mm
ICU Lenght of Stay	ICULOS	Integer	${\it Number of Days (Integer; calculated from the admission and discharge date)}$
Death	RIP	Binary	Yes/No
Readmission during study period	READ	Binary	Yes/No (if after episode)

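### The primary question on 6-month recurrence cannot be answered: readmission is recorded without date or cause, and the stated follow-up ends too early and contradicts itself

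*Protocol*

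**What the plan says.** Under Primary Research Questions, one of the five items is "Recurrence rate within 6 months". The outcome list under Primary Objective has the companion item "Re-admission within 6 months for related conditions".

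Data Collection Instrument 10 holds the only item on events after the index episode that could serve either. It is READ, labelled "Readmission during study period" with values "Yes/No (if after episode"). No readmission date and no reason for readmission is collected.

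Key Study Dates sets enrolment from 1 November 2023 to 1 May 2024, with each centre contributing "Ninety (90) consecutive day enrollment within this six (6) month window". It places the end of follow-up at 31 July 2024 and describes that date as "Final day of patient follow-up (60 days from admission on 01 may 2024"). For 1 September 2024 it states: "REDCap® database locked; this is the deadline for data submission and center inclusion". Center eligibility puts the lock at 1 November 2024 instead.

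Sites are told to look for readmissions. Methods for identifying patients lists "Use of electronic systems to flag any readmissions of patients identified and treated", and Patient follow-up asks investigators to check hospital systems within routine care.

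**The concern.** A 6-month recurrence rate needs three things: a time origin, a date for each event or for the last moment the patient was known to be event-free, and a way to tell recurrence from other readmissions. The form collects the index admission date but nothing about the readmission beyond its occurrence. This cannot be left to an analysis plan, because an analysis plan cannot use a date or a cause that was never recorded.

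The calendar adds a second problem. The end of follow-up is given by a date and by a rule that disagree, and neither gives every patient six months. What READ measures would then depend on which end date a site follows, and on any common calendar end date it would also depend on when the patient was admitted. Since Publication of data says results will be pooled, the likely product is a single rate with no defined horizon. Pooled subgroup comparisons could also be distorted if the subgroups differ in admission dates.

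**Working it through.** **Inputs.** All dates come from Key Study Dates, except the 1 November 2024 lock, which comes from Center eligibility. The 6-month clock has no stated origin. I count from admission, which is the most favourable choice for the plan, and take six months as calendar months.

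**Step 1: the plan's own figure.** 1 May 2024 + 60 days = 30 June 2024, so the stated 31 July does not reproduce. From 1 May to 31 July is 91 days, and 1 May + 90 days is 30 July. The date and the rule differ by 91 − 60 = 31 days.

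**Step 2: enrolment days that fall short of six months.** 1 November 2023 to 1 May 2024, both ends included, is 183 days. For each candidate end of observation, find the last admission date with six full months and count the later enrolment days.

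| End of observation | Last admission with 6 months | Days short (of 183) | Follow-up from admission |
|---|---|---|---|
| 60 days per patient | none | 183 (100%) | 60 days |
| 30 June 2024 | 31 Dec 2023 | 122 (66.7%) | 60–242 days |
| 31 July 2024 | 31 Jan 2024 | 91 (49.7%) | 91–273 days |
| 1 Sept 2024 lock | 1 Mar 2024 | 61 (33.3%) | 123–305 days |
| 1 Nov 2024 lock | 1 May 2024 | 0 | 184–366 days |

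The first three rows are the readings that the stated follow-up end supports. The last two assume that records are checked up to a lock date, which the protocol does not say. These are shares of calendar days, not of patients; the patient share depends on which 90-day block each centre chooses. With a 31 July close, a block starting 1 November 2023 has no day short, and one starting 1 February 2024 has every day short.

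**Step 3: why READ fails on every row.** Take a patient admitted on 1 November 2023 with observation to 31 July 2024, which is 273 days. A readmission in month eight scores yes, exactly as one in month two does. Restricting the analysis to early admissions therefore does not produce a 6-month rate. Even the 1 November row, where every patient has six months, gives windows of 184 to 366 days.

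**Step 4: illustration of size.** This is not a prediction of READ. It models SBO recurrence only, whereas READ counts any readmission. The true 6-month risk of 10% is my assumption, as are uniform admissions over the window. Let F(t) = 1 − exp(−λt^k) with F(182.5) = 0.10. Constant hazard is k = 1, λ = −ln(0.90)/182.5 = 0.000577. A front-loaded hazard is k = 0.5, λ = −ln(0.90)/182.5^0.5 = 0.00780. Averaging F over the 183 admission days gives:

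| End of observation | Constant hazard | Front-loaded |
|---|---|---|
| 60 days per patient | 3.4% | 5.9% |
| 30 June | 8.3% | 9.0% |
| 31 July | 9.9% | 9.9% |
| 1 Sept | 11.6% | 10.7% |
| 1 Nov | 14.6% | 12.1% |

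The 31 July row is near 10% only because long and short follow-up offset each other. On that row the earliest 90-day block (1 November to 29 January, mean follow-up 228.5 days) gives 12.35% (constant) or 11.1% (front-loaded). The latest block (2 February to 1 May, mean 135.5 days) gives 7.5% or 8.6%. Under a fixed 60 days per patient this spread disappears. With an assumed risk of 5% or 20% and constant hazard, the 31 July figure is 5.0% or 19.8%: the level moves and the pattern stays.

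**The case against.** The best defence is that the 60 days belong to the complication window, since Primary Objective separately sets 60 post-operative days for complications. Readmissions would then be gathered from hospital systems until the database closes. If the lock is 1 November 2024, that is exactly six months after the last admission, and no enrolment day falls short. The protocol does not say this, and Key Study Dates calls 31 July the final day of patient follow-up. Still, the lock conflict leaves the reading open, so the range of half to all enrolment days applies to the stated follow-up end and not to every conceivable reading. READ's study period is also undefined, so the readings tabulated may not be exhaustive. None of this supplies a date or a cause.

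A recurrence admitted to the same centre within its 90-day block could be entered as a new eligible patient, with its own admission date and etiology. That covers at most 90 days, and no linkage to the index record is described.

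It is also fair that the audit is descriptive and hypothesis-generating, and that recurrence is one of five primary questions. The other four do not depend on READ. But a descriptive rate needs a defined horizon as much as any other.

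Finally, the illustrative percentages rest on an assumed risk, and on the 31 July reading the pooled discrepancy is only about 0.1 point. That is why they illustrate and are not the argument.

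**Conclusion.** The concern holds and must be fixed. READ, undated and without cause, cannot yield a 6-month rate of related recurrence under any of the end dates examined. Independently of that, the stated follow-up end is internally inconsistent by 31 days and leaves 91, 122 or 183 of 183 enrolment days short of six months, depending on how it is read. The lock dates differ by two months; only the later one reaches six months for the last admission, and it leaves no time for data validation.

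The day counts rest on the protocol's dates alone, with the clock starting at admission. The direction of bias in a reported rate is not fixed, and a difference between centres is possible but not certain.

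**What to change.** First reconcile the 60-day rule with 31 July in Key Study Dates, and the lock date there with the one in Center eligibility. Then choose one of two routes.

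- **Keep six months.** State the origin (index admission or discharge), follow every patient to six months from it, run follow-up to at least 1 November 2024 (later if the clock starts at discharge), and set one lock after that. This moves the lock two to three months past 1 September and needs one more record check.
- **Keep the calendar.** Restate the outcome in Primary Objective and Primary Research Questions at a horizon every patient reaches: 90 days from admission if 31 July stands, 60 days if 30 June does. This gives up the 6-month horizon.

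On either route, expand READ to: readmitted yes/no, date of first readmission, readmission for SBO or a related condition yes/no, and date of last record check. The date and the cause are indispensable; the record-check date shows that the horizon was actually reached. Report recurrence at that fixed time point. The handling of death can be left to the SAP, but if death is to be a competing event its date must be collected, because the death item is also an undated yes/no. The cost on the form is three fields beyond the existing yes/no, or four with date of death.

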### **Secondary Research Questions**

- What is the incidence and etiology of virgin abdomen SBO?
- What is the incidence of early postoperative SBO?
- What is the success rate for non-operative management?
- What is the prevalence of complications and treatment failure in the nonoperative management of SBO?
- Proportion of patients that underwent WSOC challenge, and under what indications?
- What are the Patient Related Outcomes results?

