## Data Collection Instrument 9 - Current episode Surgery

Current Episode Surgery	Key Name	Data Type	Values
Surgery Indicated Without Non-operative Attempt	SIWA	Binary	Yes/No
Date of Surgery	DSU	Date; time	dd/mm/yy hh:mm
Time to Surgery	TTSU	Integer	Hours (calculation DSU-DOA)
Laparoscopy	LAP	Binary	Yes/No (initiated)
Conversion	LAPC	Binary	Yes/No
Operative Time	ОТ	Integer	Number (Minutes)
Single Band Adhesilysis	SBA	Binary	Yes/No
Peritoneal Adhesion Index	PAI	Integer	Number
Ischemic Bowel	IB	Binary	Yes/No
Perforated Bowel	РВ	Binary	Yes/No
Serosal Tear	SUST	Binary	Yes/No (if one at least)
Unintended Bowel Perforation	UBP	Binary	Yes/No (if handmade)
Bowel Resection	SUBR	Binary	Yes/No
Anastomosis	SUBA	Binary	Yes/No
Stoma	SUST	Binary	Yes/No
Damage control (Open Abdomen)	SUDC	Binary	Yes/No
Hernia Repair	SUHR	Binary	Yes/No

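### The protocol asks how often non-operative management leads to complications, but its only overall complication flag and its complication window are post-operative, and medical complications carry no timing relative to surgery

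*Protocol*

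**What the plan says.** Under Secondary Research Questions the Protocol asks "What is the prevalence of complications and treatment failure in the nonoperative management of SBO". The Primary Objective lists as an outcome "Complications related to disease and/or therapies within 60 post-operative days". That wording takes in complications of the disease and of any therapy, but it counts time from an operation.

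General complications are recorded in DCI 10:

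- The overall flag (POCO) is "Postoperative Complication", Yes/No, to be ticked if there is at least one. There is no non-operative counterpart.
- Four medical rows follow: "Broncoaspirative pneumonia", "New Acute Kidney Insufficiency", new-onset cardiac arrhythmia and "Deep Vein Thrombosis/Pulmonary Embolism". Each is Yes/No, without a date, and none is worded as post-operative.
- The surgical rows (three kinds of surgical site infection, anastomotic leak, reoperation) are also Yes/No.
- "Most Severe Complication" (MSCO) is free text and is followed by a Clavien-Dindo grade. Neither is dated.
- Only ICU admission and discharge carry dates.

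DCI 9 records the date and time of surgery (DSU) and "Surgery Indicated Without Non-operative Attempt" (SIWA). DCI 8 records whether non-operative treatment succeeded (COTS).

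**The concern.** The question is about harm arising under non-operative management, while the overall flag and the window are framed by surgery. Two groups of patients are affected.

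The first is patients never operated on. A post-operative window has no starting point for them. A site could reasonably read a flag labelled post-operative as not applying, and the Protocol does not say how to complete it for them.

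The second is patients who start non-operatively and are then operated on. Someone who aspirates on day 2 of non-operative care and has surgery on day 3 is coded exactly like someone who aspirates after the operation. The time of surgery is known, but there is no complication time to set against it. These are patients in whom complications of the non-operative phase are of particular interest.

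This is a fault of data capture. An analysis plan can choose a convention for attributing the events, but it cannot recover timing that was never recorded.

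**Working it through.** The Protocol states no rate or sample size on this point, so there is no figure to reproduce. The check is whether the collected fields can answer the question, group by group.

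**Step 1. Who belongs to the question, and what can be separated**

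| Group | How identified | Complications of the non-operative phase |
|---|---|---|
| Never operated on | No DSU | Separable: any medical row ticked is not a complication of surgery in this episode. Completeness depends on how sites read the POCO label. |
| Operated on after a non-operative attempt | SIWA = No, DSU present | Not separable for the four medical rows, nor for MSCO and its grade where MSCO names one of them. |
| Operated on without a non-operative attempt | SIWA = Yes | Not part of the question. |

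**Step 2. What can still be placed in the middle group**

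- Surgical site infection, anastomotic leak and reoperation can only follow an operation.
- Death in an operated patient cannot precede that operation.
- ICU admission is dated and can be compared with DSU.
- Ischemic or perforated bowel and unintended perforation are recorded separately in DCI 9.

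What remains unplaced is the four medical rows, and MSCO with its grade where it names one of them.

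**Step 3. Size of the undetermined range**

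Among patients with a non-operative attempt, let f be the share later operated on, and c the share of those with at least one of the four medical complications. If none of these arose before surgery, they add nothing to the prevalence. If all did, they add f × c. The width of the undetermined range is therefore f × c.

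Both inputs are assumptions, not figures from the Protocol:

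- f = 0.10, c = 0.20: 0.10 × 0.20 = 0.02, or 2 percentage points.
- f = 0.40, c = 0.50: 0.40 × 0.50 = 0.20, or 20 percentage points.

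The range for c is one for complications of any kind. The share with one of the four medical complications can only be equal or smaller, so these widths lean high.

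**Step 4. A worked example, again with assumed figures**

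- Of 1000 patients, 70% start non-operatively: 700.
- 30% of these are later operated on: 700 × 0.30 = 210. Never operated on: 490.
- Complications in 6% of the 490: 29.4, taken as 29.
- Complications of any kind in 30% of the 210: 63.

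With no crossover event placed before surgery, the prevalence is 29/700 = 4.1%. With all 63 placed before surgery it is (29 + 63)/700 = 92/700 = 13.1%. The difference is 63/700 = 9.0 points, which equals f × c = 0.30 × 0.30.

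The upper figure is a ceiling that would be reached only if every one of the 63 patients had a medical complication. If half did, the width would be 9.0 × 0.5 = 4.5 points.

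**Step 5. The treatment-failure half of the question**

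COTS gives success or failure, and SIWA with DSU gives surgery after an attempt. This half is answerable as the forms stand.

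**The case against.** The strongest reply is that the forms capture more than the label suggests. DCI 10 is headed as the outcome of the current episode, and surgery has its own form. The section on data completion groups DCI 10 with DCI 8 as follow-up information. The section on patient follow-up asks sites to note in-hospital complications during the admission, with no limit to operated patients. Nothing says that the individual rows open only when POCO is Yes. A comparison by initial strategy needs no onset dates: every complication in a patient who had a non-operative attempt can be counted against that strategy. The study is also a descriptive, hypothesis-generating audit, and none of its primary research questions depends on this item.

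Most of this stands, and it rules out three stronger readings that a reader might draw:

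- *That complications in never-operated patients are missed.* These patients are identifiable and their medical rows can be counted if entered. Under-recording is a risk created by the label, not something the document shows.
- *That no complication in crossover patients can be assigned to a phase.* Step 2 shows that several can.
- *That the faults all favour non-operative management.* Missing timing allows the prevalence to be set too low or too high, depending on the convention. Only under-recording in never-operated patients, if it occurs, would have a definite direction: it would lower the figure.

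What the reply does not answer is the four medical rows in crossover patients. A tabulation by initial strategy is useful, but it mixes events before surgery with events after it, so it does not give the prevalence of complications arising under non-operative management.

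**Conclusion.** The point holds in a limited form. For never-operated patients, the overall flag and the window are worded for surgery, so recording is ambiguous and possibly incomplete; the extent cannot be quantified from the document. For patients operated on after a non-operative attempt, the four medical complications, and MSCO with its grade where it names one of them, cannot be placed before or after surgery. The prevalence of non-operative-phase complications is not identified for them.

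Over the assumed ranges in Step 3 the undetermined part is 2 to 20 percentage points, and it scales directly with both assumed shares. Severity is moderate: half of one of six secondary questions is affected.

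**What to change.** - Relabel POCO as *any complication (operated or not)* and require it for every patient.
- Add one marker, *before surgery / after surgery / no surgery*, or an onset date, to the four medical rows and to MSCO. Dates on reoperation and death are not needed for this purpose.
- State the complication window from admission for patients not operated on. Key Study Dates already counts follow-up from admission.
- Report non-operative complications as those in never-operated patients plus those with onset before DSU. Beside this, tabulate all complications by initial strategy, using SIWA.

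If data collection has already closed, the timing cannot be restored by analysis. The report should then give the lower and upper bounds of Step 4 from the observed counts, with only the medical rows in the upper bound.

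The cost is slightly more data entry for patients who have a complication, drawn from notes that sites are already asked to review. If the new fields are mandatory, they count toward the rule that excludes centers with more than 5% missing data. A single marker adds less to that risk than a full date on each row.
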